3.3.4. Data analysis

3.3.4.1. Power of the study

To study the efficacy, data from the retrospective and prospective study will be analyzed jointly. For the retrospective part, approximately 5,000 patients operated on for lung cancer in the participating centers from 01/01/2016 to 12/31/2021 will be included. Based on the average of approximately 450 subjects operated on in the participating centers over 6 months during the years 2019-2021, a sample of 400 subjects eligible for enrollment in 6 months during 2022 was considered in the prospective observational study. As regards the statistical power in the analysis of the primary efficacy outcome, i.e. long-term survival, the calculation was based on an assumption of non-inferiority. The following formula was used to calculate potency in survival studies which is based on the hazard ratio [37].

$$1-\beta=\Phi(z-z_{1-\alpha}), z=(\ln(\theta)-\ln(\theta_0))\sqrt{np_Ap_Bp_E}$$

Where:

- θ_0 = hazard ratio under the null hypothesis, set equal to 1
- θ = observed hazard ratio
- pE = probability of event, i.e. death, set equal to 0.8 on the basis of epidemiological data from the ATS cancer registry
- pA = proportion of treated by robotic surgery equal to 0.12 on the basis of the data present in the SDOs for the year 2019 and of the preliminary information provided by the participating centers

pB = 1-pA

- n = sample size, equal to 5400
- Φ = distribution function of the standard normal
- A = I-type error, set equal to 0
- $1-\beta =$ statistical power

By varying the observed HR of VATS death versus the observed control group between 1.08 and 1.15, the statistical power ranged from 0.5 to 0.91. The power calculation was performed using R (v4.1.2, R Core Team 2021, Vienna, Austria.)

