3.3.4.2. Efficacy study

Since this is an observational study, all analyses must take confounding into account. For each outcome, a Direct Acyclic Graph (DAG) will be prepared, discussed by surgeons and epidemiologists, i.e. a graph that allows hypothesizing the causal relationship between intervention and outcome taking into account potential confounding factors, measurable or not. On the basis of this graph, which underlies a causal model, the variables to be included in the multinomial regression model will be selected for estimating the probability of being treated with each surgical modality as a function of potential confounders (known as propensity score). Among the variables that will be considered to define the DAGs are age, gender, performance status, treatment center and tumor characteristics. The inverse of this estimated probability will be used as weight in the regression models (inverse probability weighted, IPW) which will have the outcome as the dependent variable and the treatment modality as the independent variable: robotics, VATS and thoracotomy (reference). Differences in the duration of surgery and hospitalization will be analysed using an IPW generalized linear regression model. The 30-day odds ratio (OR) of death for VATS and robotic surgery versus thoracotomy will be estimated by means of an IPW logistic regression model. Relative survival will be evaluated using a Cox IPW model and expressed both in terms of hazard ratio (HR) and as one and 5 year survival. For inpatient reoperation, the need for conversion to thoracotomy for VATS vs. robotic surgery and major complications by type of surgery, which are expected to be rare events, a we will consider a IPW zero-inflated (Poisson or negative binomial) approach. All estimates will be presented together with 95% confidence intervals obtained from a robust standard error [39]. The same analyses, if allowed by the study number, will be repeated in the three surgical subgroups (atypical and segmental resection, lobectomy, pneumonectomy), in subjects aged less than or equal to 65 years vs. superior, in patients with performance status of 0 vs. 1 vs. 2. Sensitivity analyses will be carried out using alternative models for the probability of estimating the type of intervention.

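### The survival power of 0.50 to 0.91 is for an unweighted robotic-versus-all-others comparison; it makes no allowance for the planned inverse-probability-weighted Cox model and is probably too high for it

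*Combined protocol and SAP*

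**What the plan says.** **Power calculation (section 3.3.4.1).** Long-term survival is named as the primary efficacy outcome. Power comes from a two-group formula for the log hazard ratio that depends on the product n·pA·pB·pE. The inputs are "n = sample size, equal to 5400" (about 5,000 retrospective plus 400 prospective patients), "pA = proportion of treated by robotic surgery equal to 0.12", pB as the complement (0.88), and "pE = probability of event, i.e. death, set equal to 0.8". The result is given for hazard ratios "between 1.08 and 1.15, the statistical power ranged from 0.5 to 0.91".

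**Planned analysis (section 3.3.4.2).** A multinomial propensity model estimates each patient's probability of receiving each approach. Then "The inverse of this estimated probability will be used as weight in the regression models". Survival is analysed with a weighted Cox model that has three treatment levels and thoracotomy as reference. Results are given as 95% confidence intervals from a robust standard error. Age, gender, performance status, treatment center and tumour characteristics are candidates for the causal graph from which the propensity variables will be chosen.

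Neither section, nor any other part of the document, gives an expected weight distribution, a rule for stabilising or truncating weights, an effective sample size, or an allowance for variance inflation.

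**The concern.** The formula counts each of the 5,400 patients once, in one of two groups. The planned estimator counts them unequally: a robotic patient whose estimated probability of robotic surgery was low gets a large weight. When weights vary within an arm, that arm usually carries less information than its head count. This matters most in the smallest arm. The robotic arm has 0.12 × 5,400 = 648 patients and supplies most of the variance in any comparison involving it.

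The formula also merges VATS and open surgery into one comparator, whereas the model separates them. Section 3.4.1 needs robotic surgery compared with each.

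The power statement therefore belongs to an analysis that will not be the main one. Survival is the primary efficacy outcome, and section 3.4.3 draws the economic model's efficacy inputs from the same study. If the power is overstated, an imprecise hazard ratio may be read as evidence of no difference with more confidence than the data support.

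**Working it through.** **1. Reproducing the plan's figure**

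Inputs, all from section 3.3.4.1: n = 5,400, pA = 0.12, pB = 0.88, pE = 0.8, null hazard ratio 1.

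- n·pA·pB·pE = 5,400 × 0.12 × 0.88 × 0.8 = 456.19; square root 21.359.
- HR 1.08: ln = 0.07696; 0.07696 × 21.359 = 1.644; Φ(1.644 − 1.645) = 0.500.
- HR 1.15: ln = 0.13976; 0.13976 × 21.359 = 2.985; Φ(2.985 − 1.645) = 0.910.

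The match is exact at one-sided 5%. Two-sided 5% gives 0.376/0.847, and using the VATS share of 0.235 gives 0.691/0.988; neither matches. The type I error is printed as 0, which cannot be literal and may be lost text, so one-sided 5% is inferred from the match.

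**2. Writing the same formula by arm**

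Var(ln HR) = DE_A/(deaths in A) + DE_B/(deaths in B), and power = Φ(ln HR/√Var − 1.645).

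Robotic deaths are 648 × 0.8 = 518.4; all others 4,752 × 0.8 = 3,801.6. With both design effects at 1, Var = 0.001929 + 0.000263 = 0.002192 = 1/456.19, as in step 1. The robotic term is 88% of the total.

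**3. Adding a robotic-arm design effect (assumed; not in the documents)**

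Example with DE_A = 1.5 and DE_B = 1: Var = 1.5/518.4 + 1/3,801.6 = 0.003157; √Var = 0.05618. HR 1.08: Φ(1.370 − 1.645) = 0.39. HR 1.15: Φ(2.488 − 1.645) = 0.80.

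| Robotic-arm design effect | Power at HR 1.08 | Power at HR 1.15 |
|---|---|---|
| 1 (as stated) | 0.50 | 0.91 |
| 1.05 | 0.49 | 0.90 |
| 1.25 | 0.44 | 0.85 |
| 1.5 | 0.39 | 0.80 |
| 2 | 0.33 | 0.70 |

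Allowing DE_B up to 1.1 changes these by less than 0.01. Power drops by more than two points once the robotic design effect passes about 1.08 (HR 1.08) or 1.10 (HR 1.15).

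**4. What design effect might centre mix produce?**

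If centre alone drove the weights and centres were of equal size, the Kish design effect for the robotic arm would be mean(p) × mean(1/p), where p is a centre's robotic share. All the shares below are invented, each set averaging 12%.

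| Robotic shares by centre | Design effect |
|---|---|
| 10/14% | 1.03 |
| 9/12/15% | 1.04 |
| 8/12/16% | 1.08 |
| 6/12/18% | 1.22 |
| 5/10/21% | 1.39 |
| 5/19% | 1.52 |
| 3/12/21% | 1.86 |

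**5. Planned contrasts before any weighting loss**

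Section 3.3.4.1 expects 48, 94 and 258 of 400 patients by approach (12%, 23.5%, 64.5%). Applying that mix to 5,400 gives 648 robotic, 1,269 VATS and 3,483 open. At pE = 0.8 the deaths are 518.4, 1,015.2 and 2,786.4.

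| Contrast | Var(ln HR) | Power at HR 1.08 | Power at HR 1.15 |
|---|---|---|---|
| Robotic v open | 1/518.4 + 1/2,786.4 = 0.002288 | 0.49 | 0.90 |
| Robotic v VATS | 1/518.4 + 1/1,015.2 = 0.002914 | 0.41 | 0.83 |
| VATS v open | 1/1,015.2 + 1/2,786.4 = 0.001344 | 0.68 | 0.99 |

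Merging the comparators costs almost nothing for robotic versus open. It costs 8 to 9 points for robotic versus VATS.

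**The case against.** A reader might infer that the design fails to deliver its stated power, or that the calculation contains an arithmetic error. The documents support neither. The arithmetic is right for the comparison it describes, and 5,400 is the correct sum of its parts. The size of any weighting loss depends on weights that no section describes. Treatment center is only a candidate for the causal graph, not a committed propensity variable. With mild differences between centres the design effect is 1.03 to 1.08 and power is about 0.48 to 0.49 and 0.89 to 0.90, close to what is stated. Weighting on strongly prognostic variables need not increase variance at all. These points stand, and they are why the range starts at 1.05 and the loss is called probable rather than shown.

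It can also be said that little hangs on the figure. The retrospective cohort takes all eligible patients, so power did not set its size. The stated range already begins at 0.50. The robust 95% intervals will show whatever precision is achieved. That limits the consequence, but the plan still presents as the power of its primary efficacy analysis a number computed for a different one.

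The same calculation raises other questions that this point does not settle. It is framed so that "the calculation was based on an assumption of non-inferiority", yet it uses a "hazard ratio under the null hypothesis, set equal to 1" and gives no margin. It matches only at one-sided 5%, although two-sided 95% intervals are planned. Its result sentence names VATS while pA is the robotic share. None of these removes the mismatch described here.

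**Conclusion.** The point holds as a missing allowance. The 0.50 to 0.91 describes an unweighted 12% versus 88% comparison at one-sided 5%. The planned analysis is a three-level weighted Cox model, and nothing links the two. For the robotic contrasts the stated power is probably too high.

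One part of the size follows from the plan's own figures: robotic versus VATS has 0.41/0.83 with no weighting loss, provided the prospective group mix applies to all 5,400 patients and the death probability is the same in every arm. The rest is conditional. Over assumed robotic-arm design effects of 1.05 to 2, power for the plan's own comparison runs from 0.49/0.90 down to 0.33/0.70. The lower figures need robotic use to differ strongly between patients or centres, which the documents neither state nor rule out. They should not be read as showing that the study is underpowered by a known amount.

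**What to change.** In section 3.3.4.1:

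- Label 0.50 to 0.91 as the unweighted robotic-versus-all-others figure, to be read as an upper bound for robotic contrasts when weighting adds variance (design effect of 1 or more).
- Restate power separately for robotic versus open, robotic versus VATS and VATS versus open, over an assumed design-effect range of 1.05 to 2. State the range as an assumption and name the significance level used.

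In section 3.3.4.2, commit to reporting the effective sample size for each approach once the weights are estimated, alongside the hazard ratios.

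The cost is a paragraph and a recalculation. The stated power for the robotic contrasts becomes less favourable. No extra patients and no change of analysis model are needed.

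### The survival power of 0.50 to 0.91 is set at one-sided 5%, but the hazard ratio will be reported only with a 95% interval; at that level the same inputs give 0.38 to 0.85

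*Combined protocol and SAP*

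**What the plan says.** Section 3.3.4.1 names long-term survival as the primary efficacy outcome and says that "the calculation was based on an assumption of non-inferiority". The power formula subtracts a critical value written as the 1 − α normal quantile, which is a one-sided form. Its inputs are:

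- a "hazard ratio under the null hypothesis, set equal to 1";
- an alternative hazard ratio "between 1.08 and 1.15";
- a "probability of event, i.e. death, set equal to 0.8";
- a robotic share of 0.12, with all remaining patients (0.88) as the other group;
- 5400 patients.

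The result given is that "the statistical power ranged from 0.5 to 0.91". The value of α is not legible in the text available: it reads "I-type error, set equal to 0", most likely a decimal cut off when the PDF was read, and it is not counted here as a fault.

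Section 3.3.4.2 plans a Cox model weighted by inverse probability, with thoracotomy as the reference. On reporting it says: "All estimates will be presented together with 95% confidence intervals obtained from a robust standard error".

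**The concern.** A power figure is useful if it refers to the criterion by which the result will be judged. A 95% interval leaves 2.5% on each side, so when it is compared with a reference hazard ratio its one-sided error is 2.5% and the critical value is 1.96. A calculation at 1.645 belongs to a 90% interval, which the plan does not present.

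The figure concerned is the power for the primary efficacy outcome. A reader who takes 0.50 to 0.91 as the chance that the reported interval will exclude 1 would be too optimistic, and could give too much weight to an inconclusive survival result.

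**Working it through.** **Inputs**, all from section 3.3.4.1: n = 5400, pA = 0.12, pB = 1 − 0.12 = 0.88, pE = 0.8, null hazard ratio 1, alternative hazard ratio 1.08 to 1.15.

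**Formula**: power = Φ(z − c), where z = ln(HR) × √(n × pA × pB × pE) and c is the critical value.

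**Common factor**: 5400 × 0.12 × 0.88 × 0.8 = 456.19, and √456.19 = 21.36.

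**Step 1: reproduce the plan's figures.**

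- HR 1.08: z = 0.07696 × 21.36 = 1.644. With c = 1.645, Φ(−0.001) = 0.500.
- HR 1.15: z = 0.13976 × 21.36 = 2.985. With c = 1.645, Φ(1.340) = 0.910.

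Both stated values are recovered. Solving backwards for α from the two stated powers gives 0.0501 and 0.0500. Other levels do not fit: one-sided 10% gives 0.641 and 0.956, and one-sided 1% gives 0.247 and 0.745. The calculation was therefore run at one-sided 5%, a conclusion that does not depend on the illegible α.

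**Step 2: same inputs, critical value matching a 95% interval (c = 1.960).**

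| HR | z | Power, c = 1.645 | Power, c = 1.960 | Difference |
|---|---|---|---|---|
| 1.08 | 1.644 | 0.500 | 0.376 | 0.124 |
| 1.10 | 2.036 | 0.652 | 0.530 | 0.122 |
| 1.12 | 2.421 | 0.781 | 0.677 | 0.104 |
| 1.15 | 2.985 | 0.910 | 0.847 | 0.063 |

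The opposite tail of a two-sided test adds less than 0.0002.

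**Step 3: hazard ratio with 80% power**, from HR = exp((c + 0.842) / 21.36).

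- c = 1.645: exp(2.487 / 21.36) = exp(0.1164) = 1.12.
- c = 1.960: exp(2.802 / 21.36) = exp(0.1312) = 1.14.

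**Step 4: what the restated figure does not cover.** The formula compares robotic patients with everyone else, whereas section 3.3.4.2 compares robotic surgery and VATS each with thoracotomy. As an illustration, assume that the split section 3.3.4.1 expects for the prospective study (48 robotic, 94 VATS, 258 open, out of 400) holds for all 5400.

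- Robotic versus open: n = 5400 × 306/400 = 4131, robotic share 48/306 = 0.157. At c = 1.960 the power is 0.363 at HR 1.08 and 0.832 at HR 1.15.
- VATS versus open: n = 5400 × 352/400 = 4752, VATS share 94/352 = 0.267. At c = 1.960 the power is 0.555 and 0.968.

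None of these figures allows for the loss of precision from weighting.

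**The case against.** The best reply is that nothing has been miscalculated. The stated powers follow exactly from the printed formula, the formula is openly one-sided, and a one-sided test is normal for non-inferiority. Section 3.3.4.2 only says how estimates will be presented. It gives no rule under which a survival result counts as conclusive, so showing a 95% interval does not by itself fix the test at one-sided 2.5%.

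Most of this stands. It rules out calling the figure an arithmetic error, and it means that the interval level could be aligned to the power just as well as the reverse. It does not remove the mismatch. One-sidedness is not the complaint; the level is. A non-inferiority claim read from a 95% interval also carries a one-sided error of 2.5%, and the 95% interval is the only one the plan presents.

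A second reply also stands: 0.38 to 0.85 is not the exact power of the planned analysis either, for the reasons in step 4 of the working, and because the null hazard ratio is 1 with no margin.

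Three stronger readings are tempting, and the documents do not support them.

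- *The study is too small, or its size was derived from a wrong power.* The 5400 comes from about 5,000 available retrospective cases plus 400 prospective ones, not from a power target.
- *The cost-effectiveness results are affected.* Sections 3.4.3 and 3.4.4 take estimates and confidence limits as inputs, not power.
- *The quality-of-life power contradicts the survival power.* Its table can be matched at two-sided 5% as a robotic-versus-open contrast, but a two-sided level for a difference and a one-sided level for non-inferiority are not inconsistent in themselves.

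**Conclusion.** The point holds as a mismatch of error level between sections 3.3.4.1 and 3.3.4.2. The stated power refers to a looser criterion than the only interval the plan reports. Judged by a 95% interval against a hazard ratio of 1, power is lower by about 12 percentage points at the bottom of the stated range and 6 at the top, and the best case falls below 0.90.

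This rests on two assumptions: that the plan's other inputs are taken as given, and that the survival conclusion will be read from the 95% interval, which the plan implies but does not state. The consequence is limited to how the power statement is read.

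Two neighbouring points are separate and need their own reconciliation: the calculation is called non-inferiority but has no margin, and the hazard ratio is labelled as VATS versus control while the share entered is that of robotic surgery.

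**What to change.** Either of two changes reconciles the sections.

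1. In 3.3.4.1, state α and its sidedness and restate the power at 1.96, for example: *for hazard ratios of 1.08 to 1.15 the power ranges from 0.38 to 0.85 (two-sided 5%, matching the 95% intervals of section 3.3.4.2), before any loss from weighting; the comparison is robotic surgery versus all other patients with a null hazard ratio of 1.*
2. Keep 0.50 to 0.91 in 3.3.4.1, label it as one-sided 5%, and add to 3.3.4.2 that the survival conclusion is read from a 90% interval.

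The first is simpler because it leaves the analysis section as it is. It costs one sentence and a rerun of the R calculation, and the only drawback is a less favourable stated power. The second costs one label and one sentence, plus a 90% interval in the survival results. Neither affects patients, data collection or sample size.

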3.3.2.1. Efficacy

The evaluated outcomes will be related to two domains: -*How does technology affect the course of the disease*?

Long-term survival

-How technology affects health-related quality of life?

Descriptive analysis of EQ-5D-5L and EORCT QLQ-LC29 questionnaire results by type of approach and surgical procedure

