As regards the analysis of quality of life, the prospective study will take into consideration patients undergoing three types of surgery: robot-assisted, VATS, and open surgery. Specifically, the number of groups enrolled is assumed starting from the average of interventions carried out in the period 2016-2021. Therefore, for the prospective study, we estimated 48 subjects operated with robotic surgery, 94 with VATS, and 258 with open surgery. Literature relating to the comparison of the quality of life in patients operated with VATS and open surgery [38] illustrates the analysis of the EQ-5D questionnaire at different post-intervention time points. The data of our interest relate to the mean and standard deviation of the Visual Analogue Score of the EQ-5D questionnaire administered 4 weeks after the intervention; respectively: VATS 78.1, Open 73.5. The one-way analysis of variance methodology was used to study the power. For robotic surgery, since the necessary data in the literature are not available, we assumed an average of the Visual Analogue Score EQ-5D ranging from 80 to 83, which allowed the calculation of the estimated power illustrated in the table below. A standard deviation of 17.2 was assumed for all three groups based on literature data [38]. For the analysis of statistical power, we used the PROC POWER procedure, statement ONEWAYANOVA of the SAS software (v. 9.4, SAS Institute Inc., Cary, NC, USA).

Mean Visual Analogue Score EQ-5D	Power
80	0.669
81	0.790
82	0.880
83	0.939

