3.3.4.3. Quality of life and patient experience

Descriptive analyses will be carried out, also using bar graphs, of the items of the EQ-5D-5L and EORCT QLQ-LC29 questionnaires, comparing the pre- and post-operative values for each surgical approach. Starting from the results of the EQ-5D, the utility index associated with the health-related quality of life (HRQoL) will be calculated, and will be summarized through appropriate measures of position and variability for the three surgical approaches. Differences between surgical approach in terms of utility index will be estimated using a model for longitudinal data weighted by the inverse of the probability of surgical approach, similarly to what is described in the previous paragraph. As regards the PREMs questionnaires, descriptive analyses of the individual items will be carried out globally and by type of treatment.

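### The quality-of-life power is for a robotic-versus-open contrast in the EQ-5D VAS at 4 weeks, but the only modelled quality-of-life comparison is of the utility index, which has no power or precision statement

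*Combined protocol and SAP*

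**What the plan says.** The quality-of-life part of section 3.3.4.1 takes its inputs from the "mean and standard deviation of the Visual Analogue Score of the EQ-5D questionnaire administered 4 weeks after the intervention". The means are given as "respectively: VATS 78.1, Open 73.5". For robotic surgery, where the protocol reports no usable literature, "we assumed an average of the Visual Analogue Score EQ-5D ranging from 80 to 83". On spread, "A standard deviation of 17.2 was assumed for all three groups based on literature data". For group sizes, "we estimated 48 subjects operated with robotic surgery, 94 with VATS, and 258 with open surgery". On method, "The one-way analysis of variance methodology was used to study the power". The resulting table gives power of 0.669, 0.790, 0.880 and 0.939 for robotic means of 80, 81, 82 and 83. The section does not say which test or contrast these values belong to, and states no alpha for them.

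The analysis is in section 3.3.4.3. Questionnaire items are described before and after surgery for each approach, and the utility index is summarised by approach. One modelled comparison follows, with propensity-based weights: "Differences between surgical approach in terms of utility index will be estimated using a model for longitudinal data weighted by the inverse". The VAS is not mentioned there. Section 3.3.2.1 defines the quality-of-life outcome as "Descriptive analysis of EQ-5D-5L and EORCT QLQ-LC29 questionnaire results by type of approach and surgical procedure". Section 3.4.2 names the VAS beside the utility index under the societal viewpoint, without a model or test.

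**The concern.** The VAS and the utility index come from the same questionnaire but are different variables. The VAS is a self-rating on a scale of 0 to 100. The index is calculated from the EQ-5D responses with a scoring function and Italian reference values (section 3.4.3). A standard deviation and a difference on one do not carry over to the other, and the documents supply them only for the VAS.

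Two things follow. The outcome with a stated power has no specified model for differences between approaches. The outcome that is modelled, and that feeds the QALYs and the cost-utility ratio, has no statement of what difference it could detect. A reader who takes 0.669 to 0.939 as the power of the quality-of-life comparison could treat a null result on the utility index as evidence from a well-powered comparison, which the documents do not support.

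**Working it through.** **Inputs (all from section 3.3.4.1).** Group sizes 48 robotic, 94 VATS and 258 open, total 400. Means 78.1 (VATS), 73.5 (open) and 80 to 83 (robotic). Common SD 17.2. Alpha is not stated for this calculation; I assume 0.05 two-sided.

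**Step 1: reproduce the printed powers.** For a contrast of two groups within a one-way ANOVA:

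- SE = SD × √(1/n₁ + 1/n₂), with error df = 400 − 3 = 397 and a critical t of 1.966
- noncentrality = difference / SE
- power from the noncentral t distribution

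Robotic versus open: SE = 17.2 × √(1/48 + 1/258) = 17.2 × 0.1572 = 2.704.

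| Robotic mean | Difference from open | Noncentrality | Power | Printed |
|---|---|---|---|---|
| 80 | 6.5 | 2.404 | 0.669 | 0.669 |
| 81 | 7.5 | 2.774 | 0.790 | 0.790 |
| 82 | 8.5 | 3.144 | 0.880 | 0.880 |
| 83 | 9.5 | 3.514 | 0.939 | 0.939 |

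All four match to three decimals. The arithmetic is sound and the assumed alpha is confirmed indirectly.

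**Step 2: rule out the overall test.** The three-group F test at 0.05 gives 0.762, 0.834, 0.893 and 0.938, which misses the first two printed values clearly. The same F test at alpha 0.10, 0.025 or 0.01, and equal groups at 0.05, also fail to give the table.

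**Step 3: the other two contrasts on the same inputs.**

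- Robotic versus VATS: SE = 17.2 × √(1/48 + 1/94) = 3.051. Differences of 1.9, 2.9, 3.9 and 4.9 give power of 0.095, 0.158, 0.247 and 0.360.
- VATS versus open: SE = 17.2 × √(1/94 + 1/258) = 2.072. The difference of 4.6 gives power of 0.600.

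**Step 4: what can be said about the utility index.** Its power cannot be computed, because no SD or target difference is given. What the group sizes allow is a detectable difference in SD units at 80% power, (1.960 + 0.842) × √(1/n₁ + 1/n₂), for a single time point without weighting:

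| Contrast | Detectable, in SDs | If utility SD is 0.10 to 0.25 (assumed) |
|---|---|---|
| Robotic vs open | 0.44 | 0.044 to 0.110 |
| Robotic vs VATS | 0.50 | 0.050 to 0.124 |
| VATS vs open | 0.34 | 0.034 to 0.084 |

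For comparison, the VAS assumptions for robotic versus open amount to 6.5/17.2 = 0.38 to 9.5/17.2 = 0.55 SD. Whether the utility index would show a difference of that size is not addressed.

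**Step 5: the form of the analysis.** The calculation is for one time point, unweighted, with all 400 expected patients contributing. The plan is a longitudinal model weighted by inverse probabilities, with questionnaires completed by patients at days 7 and 30 (section 3.3.2). No allowance is made for precision lost through weighting or for missing questionnaires.

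**Step 6: does another section supply a VAS model?** Section 3.3.4.2 describes weighted outcome models in general terms, then names the outcomes: durations, 30-day death, survival, reoperation, conversion and complications. The VAS is not among them. Sections 3.3.2.1 and 3.4.2 add description and a mention, but no model.

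**The case against.** The case for leaving the plan alone has several parts.

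First, a reader might infer that the VAS is never compared between approaches or never used. That goes too far. Section 3.3.2.1 plans descriptive EQ-5D-5L results by approach, and section 3.4.2 names the VAS in an evaluation that compares the three approaches. What is absent is a specified model for the VAS. Nor is adjustment ruled out, since section 3.3.4.2 requires every analysis to deal with confounding; for the VAS, how that would be done is simply not written down.

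Second, little depends on the printed power. The 400 patients come from expected caseload over six months, section 3.3.4.3 speaks of estimating differences, and there is no success rule for quality of life. The text and the table header both label the values as VAS. All of this stands and limits the consequence. It does not supply a precision statement for the outcome that is modelled.

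Third, the utility index is the natural outcome to model in a study built on cost per QALY. I agree. The documents give no reason to make the VAS the main quality-of-life comparison, and that would be a preference about endpoints. A reader might also argue that the VAS is the only outcome with a published difference between VATS and open surgery at this time point. The documents cannot support that: section 3.3.4.1 says only which data it took from the cited trial, and that trial may report the index too.

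**Conclusion.** The mismatch is real. The power of 0.669 to 0.939 describes an unweighted robotic-versus-open contrast in the VAS at 4 weeks, for which section 3.3.4.3 specifies no model. The utility index, the only quality-of-life outcome modelled between approaches, has no stated SD, target difference or power.

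The table also says less than it appears to. On its own inputs, power is 0.095 to 0.360 for robotic versus VATS and 0.600 for VATS versus open, so it cannot stand for the comparison of approaches in general, even on the VAS.

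These figures rest on the protocol's means, SD and group sizes and on a two-sided alpha of 0.05, which is assumed but reproduces all four values. A reader might conclude that the utility comparison is underpowered. The documents do not show that; they leave its power unknown. The survival analysis is not affected.

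**What to change.** In section 3.3.4.3, add the EQ-5D VAS as a further outcome of the same inverse-probability-weighted longitudinal model, and report the day-30 differences between approaches with 95% confidence intervals. Keep the utility index as the QALY input.

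In section 3.3.4.1, state that:

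- the printed powers apply to the day-30 VAS, robotic versus open only, at the alpha used, with no allowance for weighting or missing questionnaires;
- on the same inputs, power is 0.095 to 0.360 for robotic versus VATS and 0.600 for VATS versus open;
- the values do not apply to the utility index, for which a null result is to be read from its confidence interval.

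The cost is one extra run of a model already planned, on data already collected, and a few sentences of text. The downside is that the protocol would then show low power for two of its three VAS contrasts.
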